### ***10.3 Audit and Inspection***

This study may be audited by representatives from the coordinating centre and sponsor. The investigator and institution will be informed of the audit outcome. Investigators are obliged to cooperate in any audit allowing the auditor direct access to all relevant documents and allocate his/her time and the time of his/her staff to the auditor to discuss any findings or issues. Audit may occur at any time during or after completion of the study.

In addition, inspections may also be carried out by the Competent Authority at any time and the investigator should notify the sponsor **immediately** if there are any such plans for an inspection.

### ***10.4 Serious breaches in GCP or study protocol***

All investigators participating in the study will promptly notify the Chief Investigator or Sponsor of a serious breach as soon as they become aware. This is defined in Regulation 29A of the Medicines for Human Use (Clinical Trials) Regulations 2004 [Statutory Instrument 2004/1031], as amended by Statutory Instrument 2006/1928 and contains the requirements for notifying serious breaches of GCP or study protocol. The CI is then responsible for notifying the Sponsor within 1 working day of becoming aware of a serious breach.

The sponsor (JRMO) is responsible for notifying the licensing authority in writing of any serious breach of:

- (a) The conditions and principles of GCP in connection with that trial; or
- (b) The protocol relating to that trial, as amended from time to time in accordance with regulations 22 to 25, within 7 days of becoming aware of that breach.

A “serious breach” is a breach which is likely to affect to a significant degree:-

The safety or physical or mental integrity of the subjects of the trial; or the scientific value of the trial.

Participating centres should contact the coordinating centre or CI for further information.

#### **10.5 *Quality Assurance***

This study will be conducted in accordance with the Centre of Experimental Cancer Medicine standard operating procedures and those of the sponsor.

#### **10.6 *Ethical Considerations***

The study will be conducted in accordance with ethical principles founded in the Declaration of Helsinki. An independent Ethics committee (IEC) will review all appropriate study documentation in order to safeguard the rights, safety and wellbeing of patients. The study will only be conducted at sites where appropriate approval has been obtained.

The study coordinating team will inform the IEC of any changes to the conduct of the study and seek approval for these changes and any amended patient materials. The Chief investigator will maintain an accurate and complete record of all written correspondence to and from the IEC and will agree to share all such documents and reports with the sponsor.

The informed consent and any other documentation provided to subjects will be revised if important new information becomes available that is relevant to the subject's consent. Amended documents will be approved by the IEC before distribution to patients.

## **10.7 *Trial Committees***

### **10.7.1 Trial Steering Committee (TSC)**

A Trial Steering Committee will be convened and will provide an internal review of the conduct of this clinical trial to ensure continuing patient safety as well as the validity and scientific merit of the trial.

Details of the Trial Steering Committee will be described in the TSC remit and will be updated if any change occurs during the course of the study. The TSC remit will be provided to all members. Details of the frequency of the meetings and the information held will be described in the TSC remit.

### **10.7.2 Trial Management Group (TMG)**

Details of the trial management committee will be described in the TMG remit and will be updated if any change occurs during the course of the study. The TMG remit will be provided to all members.

The Trial Management Group will consist of, as a minimum, the Chief Investigator, Statistician, and Trial Co-ordination staff. They will be responsible for the day-to-day running and management of the trial. The frequency of the meetings and the information held will be described in the TMG remit.

## 11 Statistics

### 11.1 Endpoints

#### 11.1.1 Primary Endpoints

- 2-year Progression free survival

#### 11.1.2 Secondary Endpoints

- Metabolic response
- Overall survival
- Toxicity level (CTCAE version 4.03)

#### 11.1.3 Definition of end of study

Patients will be recruited for 48 months. Patients will be followed up as part of the study for 2 years following completion of treatment. The end of the study will be 3 months after the date when the last patient has completed his final follow up visit.

## 11.2 Statistical considerations

### 11.2.1 Sample Size

The primary objective is to gain a preliminary indication on whether carboplatin AUC-10 is worthwhile considering in a phase III study, using the progression free survival (PFS) rate as a criterion. A'Hern's single-stage procedure is used to estimate the number of patients required [8].

The primary outcome is the percentage of patients progression-free at 2-years. Therefore, all patients must have at least 2-years follow-up (unless they have died or their disease has progressed). An MRC study [1] showed that PFS rate at 3 years in standard chemotherapy, BEP, is 81%. It is also known that PFS rate at 2-years and 3-years are the same [2]. Carboplatin AUC-10 should not therefore have a 2-year PFS rate of 75% or less, and it would only be worth considering in a phase III study if the true rate were 90% or more. This information is used in A'Hern's single stage design to yield a sample size of 45 patients, with 80% power and one-sided test of significance at the 5% level. Here the statistical assumption of this design is that there is 80% chance of concluding that Carboplatin AUC-10 is effective if the true response rate is 90% or more, but only a 5%

chance of concluding it is effective if the response rate is 75% or less. To allow for a 10% drop-out rate the intention is to recruit 50 patients.

### **11.2.2 Planned recruitment rate**

It is planned to have the study performed at approximately 4 centres to recruit around 10-12 patients per year. Assuming 5 patients may withdraw from the study for reasons other than disease progression/intolerable side effects, up to 50 patients may be entered in total. In the event that the first centres initiated are not able to recruit sufficient patients, further centres may be recruited. Total duration of study recruitment is approximately 4 years.

### **11.3 Statistical Analysis**

All analyses in this study are descriptive and exploratory by nature. Results will be summarised with descriptive statistics (i.e. sample size, mean, and standard deviation, minimum, maximum and median for continuous variables and with tabulations/frequency tables/case listings for categorical variables). Incidence of adverse events will be tabulated. Laboratory data will also be analysed and summarised.

Two analysis sets will be defined:

- The Full Analysis Set (FAS) will consist of all patients who completed at least one cycle of Carboplatin AUC-10 and for whom relevant data is available at baseline and follow up.
- The Safety analysis set (SS) will consist of all patients who received at least one dose of Carboplatin AUC-10.

The FAS will be used for all activity summaries; the SS will be used for all safety summaries. Further descriptions of the statistical analyses will be given in the Study Statistical Analysis Plan, to be finalised prior to database lock.

### **11.4 Frequency of analysis**

The data will be analysed at the end of the study. There will be no interim analysis.

### **11.5 Primary endpoint analysis**

The primary efficacy endpoint is Progression Free Survival (PFS) rate at 2 years. Patients who do not complete 2 years follow-up for reasons other than death will be censored at the last date of follow-up. The PFS rate will be determined for the Carboplatin AUC-10, along with a 95% confidence interval, and the Kaplan-Meier curves will be plotted. The study result will be considered positive if the PFS rate for patients on Carboplatin AUC-10 is consistent with a true difference of 15% or more from standard chemo i.e. if there are at least 39 PFS patients out of the first 45 patients at 2 years.

### **11.6 Secondary endpoint analysis**

Subgroup analyses of the PFS rate will be performed in terms of patients with complete or partial response at 2 years.

The analysis of safety will include all patients who received at least one cycle of treatment. Safety and tolerability of Carboplatin AUC-10 will be assessed in terms of changes in laboratory parameters, vital signs, the incidence and severity of Adverse Events, and of toxicities according to the CTCAE classification (version 4.03).

The proportion of patients at each toxicity grade (0 to 4) of any type (including vomiting, nausea and diarrhoea) will be summarised. Safety analysis will be performed based on safety data set.

Metabolic response rate will be assessed as described in section 5.3.3.

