Statistical Methodology and Analysis	
The primary efficacy endpoint is the Progression Free Survival (PFS) rate at 2 years from completion of treatment. Patients who do not complete 2 years follow-up for reasons other than death will be censored at the last date of follow-up. The PFS rate will be determined for the Carboplatin AUC-10, along with a 95% confidence interval, and the Kaplan-Meier curves will be plotted. The trial result will be considered positive if the PFS rate for patients on Carboplatin AUC-10 demonstrates an increase in survival of 15% or more when compared to PFS rates of standard chemo i.e. if there are at least 39 PFS patients out of first 45 patients at 2 years.
 
Subgroup analyses of the PFS rate will be performed in terms of patients with complete or partial response at 2 years. The analysis of safety will include all patients who received at least one cycle of treatment. Safety and tolerability of Carboplatin AUC-10 will be determined by an evaluation of changes in laboratory parameters, vital signs, the incidence and severity of Adverse Events and of toxicities according to the CTCAE classification (version 4.03). The proportion of patients at each toxicity grade (0 to 4) of any type (including vomiting, nausea and diarrhoea) will be summarised. Safety analysis will be performed based on safety data set.
 
Metabolic response rate will be assessed as described in section 5.3.3 of the protocol.

---	--

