### **2.0 Study aims and objectives**

- To assess the safety, efficacy and toxicity of carboplatin AUC-10 in metastatic seminoma in a multi-centre setting.
- To see if, by using FDG PET-CT to assess metabolic response, the number of patients requiring 4 cycles can be reduced.

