**APPENDIX 2 – PET-CT RESPONSE DEFINITIONS FOR CLINICAL TRIALS\***

RESPONSE	DEFINITION	NODAL MASSES
CR	Disappearance of all evidence of disease	a. FDG-avid or PET positive prior to therapy; mass of any size permitted if PET negative b. Variably FDG-avid or PET negative; regression to normal size on CT
PR	Regression of measurable disease and no new sites	>50% decrease in SPD of up to 6 largest dominant masses; no increase in size of other nodes a. FDG-avid or PET positive prior to therapy; one or more PET positive at previously involved site b. Variably FDG-avid or PET negative; regression on CT
SD	Failure to attain CR/PR or PD	a. FDG-avid or PET positive prior to therapy; PET positive at prior sites of disease and no new sites on CT or PET b. Variably FDG-avid or PET negative; no change in size of previous lesions on CT
RELAPSED DISEASE OR PD	Any new lesion or increase by >50% of previously involved sites from nadir	Appearance of a new lesion(s) >1.5 cm in any axis, >50% increase in SPD of more than one node, or >50% increase in longest diameter of a previously identified node >1cm in short axis Lesions PET positive if FDG-avid lymphoma or PET positive prior to therapy

Abbreviations: CR, complete remission; FDG, [F] fluorodeoxyglucose; PET, positron emission tomography; CT, computed tomography; PR, partial remission; SPD, sum of produce of the diameters; SD, stable disease; PD, progressive disease.
		

\*As published in Journal of Clinical Oncology [6]

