### **COMPLETE RESPONSE (CR)**

Normal tumour markers, no clinical or radiological evidence of disease or surgery indicating no viable cancer cells in resected specimens (if surgery is done at this stage).

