### **PARTIAL RESPONSE (PR) (marker negative)**

Normalisation of markers and residual mass (marker negative PR) for at least 28 days

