3.4 Study Variables

3.4.1 Primary and Secondary Variables

3.4.1.1 Primary Efficacy Variables

3.4.1.1.1 Progression-Free Survival (PFS)

PFS is defined as the time between the date of enrolment to first evidence of disease progression based on central review or death, whichever occurs first. For patients who have not died or experienced disease progression at the end of study, PFS will be censored on the last date the patient was known to be progression-free. Patients with no post-baseline tumour assessment will be censored at the date of enrolment plus 1 day. The PFS time will always be derived based on scan/assessment dates not visit dates.

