7.3 Secondary Efficacy Analysis

7.3.1 Metabolic Response Rate

The number and percentage of subjects falling into each response category defined in Appendix 2 of the protocol i.e. the categories of: CR, PR marker positive, PR marker negative, stable disease, and progressive disease after one cycle will be descriptively tabulated.

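### The planned PFS subgroup analysis groups patients by response at 2 years: read literally it is circular with the endpoint, and read the other way it lacks a landmark

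*Protocol*

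**What the plan says.** Protocol section 11.6 states: "Subgroup analyses of the PFS rate will be performed in terms of patients with complete or partial response at 2 years". The synopsis repeats the sentence.

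The endpoint being subdivided is 2-year PFS. The SAP (section 3.4.1.1.1) gives the event and clock: "PFS is defined as the time between the date of enrolment to first evidence of disease progression based on central review or death". The synopsis uses a different clock: "Progression Free Survival (PFS) rate at 2 years from completion of treatment". Protocol section 11.5 names no origin.

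No section defines a response assessed at 2 years:
- Protocol Appendix 3 defines conventional response around the end of chemotherapy. Complete response includes "no clinical or radiological evidence of disease". Marker-negative partial response is "Normalisation of markers and residual mass (marker negative PR) for at least 28 days".
- Protocol Appendix 2 defines PET-CT partial response as "Regression of measurable disease and no new sites".
- SAP section 7.3.1 tabulates metabolic response categories up to "progressive disease after one cycle will be descriptively tabulated".
- SAP section 2 takes overall response at the end of treatment.

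SAP sections 7.2 and 7.3 contain no PFS analysis by response.

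**The concern.** A subgroup should be defined by something known before the outcome is decided. Here the sentence can be read as grouping patients by their disease status at 2 years, while the outcome is whether they progressed or died by 2 years. Both definitions of response require absence of new or visible disease, so the grouping largely restates the outcome. The table would show a strong link between response and PFS even if the drug did nothing.

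The other reading takes response at some earlier time and reports 2-year PFS in responders. A patient must then stay event-free long enough to be assessed as a responder, and that waiting time is credited to responders when PFS runs from enrolment. No response time point and no landmark are stated.

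The protocol's second aim is "To see if, by using FDG PET-CT to assess metabolic response, the number of patients requiring 4 cycles can be reduced". Outcome by the first-cycle PET-CT result is therefore a natural table for readers to look for. No planned analysis supplies it.

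**Working it through.** **1. The plan's own figure.** Inputs from Protocol section 11.2.1: null rate 75%, target 90%, one-sided 5%, 80% power, n = 45. Section 11.5 gives success at 39 or more. Exact binomial:
- P(X ≥ 39 | 45, 0.75) = 0.0446
- P(X ≥ 39 | 45, 0.90) = 0.841
- 45 / 0.9 = 50 to recruit

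The design reproduces. The subgroup sentence does not enter any of these figures.

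**2. Literal reading, uninterrupted response.** Response at 2 years then implies no progression and no death by 2 years, so P(progression-free at 2 years | response at 2 years) = 1. A simulation with exponential progression times gives 100% in responders at a true rate of 75% and at 90%.

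The choice of clock barely changes this. Response 2 years after treatment implies progression-free at 2 years from enrolment. Only if response is read 2 years from enrolment and PFS 2 years from completion are the last weeks left open (about 9 to 12, from 3 or 4 cycles of 3 weeks).

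**3. Literal reading, salvaged patients counted.** Protocol section 1.3 reports that earlier relapses (2 of 40) were salvaged. Let s be the assumed share of progressors who are in remission after salvage at 2 years and are classed as responders. With 39 progression-free, all in response, and 6 progressed:

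responder PFS = 39 / (39 + 6s)

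| s | Responder 2-year PFS |
|---|---|
| 0 | 39/39 = 100% |
| 0.5 | 39/42 = 92.9% |
| 1 | 39/45 = 86.7% |

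The result moves with a classification rule that neither document gives.

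**4. Alternative reading, earlier response and PFS from enrolment.** The first-cycle scan is at day 17–21, about 3 weeks. End of treatment is 3 × 3 = 9 or 4 × 3 = 12 weeks. As a share of 104 weeks, 3/104 = 2.9% and 12/104 = 11.5%.

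To size the effect, assume a constant hazard and response unrelated to progression. With true 2-year PFS p and assessment at week w, the probability of reaching the assessment event-free is p^(w/104), and responder PFS = p / p^(w/104).

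| True p | w = 3 | w = 12 |
|---|---|---|
| 75% | 0.75/0.9917 = 75.6% | 0.75/0.9674 = 77.5% |
| 90% | 0.90/0.9970 = 90.3% | 0.90/0.9879 = 91.1% |

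The distortion in responders is small. It is larger in a small comparison group that absorbs the early progressors. If 90% of assessed patients respond (assumed) and p = 75% at week 12, non-responder PFS is (0.1 × 0.75) / (0.1 × 0.9674 + 0.0326) = 58.0%, although response has no effect.

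Without the guaranteed time, the artefact disappears. Simulating response with the same 90% share, unrelated to progression and without requiring patients to survive to assessment, gives about 75% in both groups at a true rate of 75%, and about 90% in both at 90%.

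**5. Can response at 2 years be observed?** Protocol section 5.3.2 and note 7 of the study flowchart schedule a 2-year CT for complete responders. No 2-year scan is scheduled for patients left in partial response, so that category would not be reliably ascertained.

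**The case against.** The strongest reply is that the literal reading is the less likely one. The documents place response after one cycle or around the end of treatment and habitually speak of the PFS rate at 2 years, so the sentence probably means 2-year PFS in patients who responded. On that reading nothing is 100% by construction. With the synopsis clock, which starts at completion of treatment, guaranteed time largely disappears. If the contrast is complete against partial response, both groups must reach the same assessment and carry similar guaranteed time. This stands as far as it goes, but it leaves the response time point unstated, and the SAP's clock starts at enrolment.

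A reader might infer that responders must show 100% and everyone else about 0%. The documents do not support either figure without a further assumption. A relapsed patient salvaged into remission could be a responder at 2 years with a PFS event. Patients with stable disease or censored follow-up fall in the remainder without having progressed.

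It is also fair that Protocol section 11.3 calls all analyses descriptive and exploratory and leaves further description to the SAP, which omits this one. The SAP heading for changes to the protocol shows no text in the copy reviewed, but that is not safe evidence of intent. What can be shown is that the two documents differ and that nothing visible in the SAP withdraws the analysis.

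Finally, a reader might infer that the trial should compare 3 with 4 cycles in this table. It cannot: cycle number is assigned by response, and the stated aim concerns how many patients need 4 cycles. Nor is an incomplete response the same as receiving 4 cycles, because Protocol section 3.1 sends patients with no response to cisplatin-based therapy.

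**Conclusion.** The concern holds in qualified form. Each reading of the sentence has a defect:
- **Literal reading:** circular. Responder PFS is 100% if response must be uninterrupted, and lies between 100% and the overall rate (86.7% at 39/45) if salvaged patients count.
- **Alternative reading, PFS from enrolment:** not predetermined, but responders carry about 3 to 12 weeks of guaranteed time. Under a constant hazard this adds at most about 2.5 percentage points to responder PFS at a true rate of 75%, and it can depress a small non-responder group much more.

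The salvage shares, the constant hazard and the 90% response share are assumptions, not figures from the documents. The primary decision rule and sample size are untouched. This is worth correcting before analysis because an analyst would otherwise have to run a table that cannot be interpreted or depart from the protocol without saying so.

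**What to change.** Replace the sentence in Protocol section 11.6 and the synopsis, and carry the replacement into SAP section 7.3:
- **Groups:** centrally reviewed metabolic response on the first-cycle PET-CT, as complete, responding but not complete, and no response shown separately. Patients withdrawn after at least one cycle remain in follow-up under Protocol section 4.4.1.
- **Clock:** 2-year PFS measured from the date of that scan, in patients still progression-free then.
- **Presentation:** Kaplan-Meier estimates with confidence intervals, or exact intervals if 2-year status is known for everyone. No between-group test.
- **Caveat to state:** the groups do not isolate the effect of 3 versus 4 cycles, because cycle number follows response.

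Alternatively, withdraw the analysis formally in both documents.

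The cost is a short edit in each document. No new data are needed: Protocol section 10.2 already lists metabolic response, number of cycles and progression dates for source verification in all patients. The downside is that patients who progress before the scan drop out of this table. Precision will also be modest: with an assumed 25 complete metabolic responders and 23 progression-free, the estimate is 23/25 = 92% with an exact 95% interval of 74.0% to 99.0%.

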### **11.7 Interim analysis**

No interim analyses are planned as the Carboplatin AUC-10 is considered to be relatively safer than the standard chemotherapy.

## **12 Sponsorship and Indemnity**

Barts Health NHS Trust is the sponsor and will be providing indemnity for this study.

## **13 Publication policy**

This is an investigator-led study sponsored by the CI's substantive employer, Barts Health NHS Trust. The data collected will not be used to licence/register any pharmaceuticals.

Authorship of the final manuscript(s), interim publications, or abstracts will be decided according to active participation in the statistical design, Trial Steering Committee, accrual of eligible patients and statistical analysis.

Contributing centres (and participating investigators) will be acknowledged in the final manuscript, and the correct designation for this site is 'Centre for Experimental Cancer Medicine, Barts Cancer Institute, Queen Mary University of London'. Representative for the sponsor will be added, as appropriate, as co-authors. No participant may present data from his/her centre separately from the rest of the study results unless approved by the Trial Steering Committee and the sponsor.

